4. BACKGROUND AND RATIONALE

Peripheral Arterial Disease (PAD) affects a fifth of people over the age of 60 in the United Kingdom (UK)(1-3). It is the commonest cause of lower limb amputation(4). Patients with PAD who develop symptoms present either with pain when walking, called intermittent claudication, or chronic limb threatening ischaemia, a condition characterised by constant pain in the leg and/or gangrene. More than half of patients who have chronic limb threatening ischaemia or intermittent claudication are expected to die, have an amputation or a major cardiovascular event i.e. heart attacks or strokes, within five years (2, 5-8). The number of people with PAD is expected to rise in the next few years, due to a sedentary life-style, poor dietary choices, rising prevalence of diabetes and longer life-expectancy(3, 9, 10).

Approximately 5% of individuals between the age of 55 and 74 have intermittent claudication or chronic limb threatening ischaemia in the UK (1, 2, 6-8, 10). In patients with chronic limb threatening ischaemia the one-year risk of limb amputation is 30% and five-year all-cause mortality is 50%, similar to various advanced forms of cancer (1, 2, 5-8, 11). Patients with chronic limb threatening ischaemia require urgent revascularisation (restoration of blood flow) in order to save their leg (prevent amputation). Overall, 27,465 leg amputations took place in patients with PAD between 2015 and 2018 in the UK(12). A timely and successful lower limb revascularisation is required to prevent these amputations and subsequent impact on patients' autonomy, quality-of-life and future health problems(3, 5, 16, 17).

An angioplasty is a procedure where an artery is opened using wires and balloons. It is the most common procedure offered to patients with PAD, especially those with limb threatening ischaemia, and it is recommended by international guidelines(18). Many factors can affect how long the arteries treated with angioplasty can remain open for(19). Calcium in the artery is one of the main factors which might cause a new blockage in an artery treated with angioplasty(20). Our research group has previously reported that the percentage of calcified plaque independently predicts restenosis at one year after angioplasty and the absolute volume of calcium was associated more amputation(23).

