6.2 Primary and Secondary Endpoints/Outcome Measures

Primary outcome measure: patency of the treated arterial atherosclerotic lesion based on duplex ultrasound measurement at six months after the procedure has taken place (recorded as a binary outcome i.e. yes or no).

Secondary outcome measures:

During the inpatient stay:

Additional treatments during the index procedure, including other endovascular treatments (e.g. application of stent or drug coated balloon therapy or any other intervention deemed necessary by each operator)

All complications during the in-hospital stay:

Duration of in-hospital stay.

Thirty days after the procedure and at six months (final follow-up):

Re-intervention (open or endovascular - including re-intervention for other indications, which will be reported separately)

Lower limb amputation

Change in the treated atherosclerotic plaque consistency for patients requiring re-intervention or having additional imaging due to re-stenosis (secondary outcomes)

Patients' quality-of-life.

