*Plaque analysis will be performed on the routine CT scans obtained at baseline. Additional plaque analysis will be undertaken on any additional CT angiograms which have been undertaken on any patient, for any reason during the six month follow-up period. We will use the scans in order to assess plaque volume (at any arterial segment treated with intravascular lithotripsy) and detailed plaque composition using a technique which our group pioneered and validated, described in detail before(23, 24). All PIs will be trained by the CI and [name] in this technique prior to commencing the study, using software which is already available at each clinical site (Aquarius TeraRecon). The scans will be analysed locally within seven days and we will report the following for each atherosclerotic plaque (i.e. target of intravascular lithotripsy treatment): volume of plaque which is calcified / fibro-calcific / fibrotic, lumen volume, plague volume, plague length. We will also report which vessels are patent and/or stenosed and/or occluded below the origin of the ipsilateral common iliac artery as well as the length (in mm) of each occluded segment. Inter- and intraoperator variability will be calculated and reported for the first five scans at each site (the CI and [name] will report the first five scans performed at each site together with the local PIs). Further, for each patient taking part we will report and record the Peripheral Arterial Calcium Scoring System (PACSS), a validated method to report degree of calcification, both before and after treatment(25).

The only study related data that is not collected as part of routine care is the completion of the EuroQol-5D (EQ-5D) questionnaire in relation to quality of life. The completion of a quality of life

CONFIDENTIAL Page 18 of 35 SHOCC Study IRAS: 299307

survey will be requested from all participating patients at baseline (pre-op) and at 6 months post discharge during their routine appointments.

Considerations due to COVID-19

We expect that COVID-19 will not have a major impact on inpatient and/or outpatient pathways for chronic limb threatening ischaemic and severe symptomatic PAD (our target population), given that these vascular pathologies are limb and/or life threatening. This has already been documented in our international study of vascular care during the COVID-19 pandemic (see: https://vascular-service-study/)

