Patient involvement in this study falls alongside routine care and there is therefore no further risk of exposure to COVID-19 due to additional hospital visits as a result of taking part in this study.

Patients and staff will follow local trust COVID guidelines on the use of face masks and social distancing when they attend their routine hospital appointments.

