8.7 Definition of End of Study

The end of study is the date of the last visit/ telephone follow up/ home visit of the last participant i.e. six months after the date the last patient has been recruited.

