11.3 The Level of Statistical Significance

A p value of <0.05 will be regarded as statistically significant.

11.4 Criteria for the Termination of the Study.

Given that this is an observational study which is recruiting patients who undergo a treatment that is already available in the NHS, we do not have specific stoppage criteria at this point in time. A Data Safety Monitoring Committee (DSMC) will convene at regular intervals, chaired by an independent specialist.

11.5 Procedure for Accounting for Missing, Unused, and Spurious Data.

The PI will be contacted at each site in case of missing or spurious data to ensure that the information collected is precise.

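### The six-month EQ-5D is tied to routine appointments and no other route is stated, so the quality-of-life summary may lean towards fitter patients

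*Protocol*

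**What the plan says.** Section 6.2 of the protocol lists "Patients' quality-of-life" among the secondary outcome measures at thirty days and six months. Section 8.3.1 includes the EQ-5D among the six-month items and then explains how it is obtained: the "survey will be requested from all participating patients at baseline (pre-op) and at 6 months post discharge during their routine appointments". Just before that it states: "The only study related data that is not collected as part of routine care is the completion of the EuroQol-5D (EQ-5D) questionnaire". The COVID-19 paragraph of the same section relies on there being no extra attendances: "there is therefore no further risk of exposure to COVID-19 due to additional hospital visits as a result of taking part in this study".

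Appendix A marks two things at six months, the questionnaire and a review of medical records. Section 8.7 mentions other forms of contact, but only in defining when the study ends: "The end of study is the date of the last visit/ telephone follow up/ home visit of the last participant". For missing data, section 11.5 says: "The PI will be contacted at each site in case of missing or spurious data". Section 11.2 expects all 60 patients to complete follow-up.

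**The concern.** Most six-month items can be taken from the notes whether or not the patient comes to clinic. The EQ-5D cannot: it exists only if someone puts it to the patient. If the one stated occasion is a routine appointment, a missed appointment means a missing score, and a query to the site investigator cannot recover answers that were never requested.

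Attendance is unlikely to be unrelated to health. Patients who are housebound, readmitted or recovering from further surgery are plausibly less likely to keep a routine outpatient appointment. The baseline reading does not face the same filter, because every participant is in contact with the team for consent and the procedure. The six-month summary could therefore look better than the cohort's true state. In a single-arm study no control group offsets that shift, and section 4 says the results are meant to help plan a randomised trial.

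**Working it through.** The protocol gives no expected EQ-5D score, standard deviation or completion rate, so there is no figure of its own to reproduce. The check has two parts.

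**1. Is there any other stated route to a six-month score?**

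- Section 8.3.1, data-collection list: names the EQ-5D at six months, with no mode of collection.
- Section 8.3.1, EQ-5D note: ties the request to routine appointments.
- Section 8.3.1, COVID-19 paragraph: no additional hospital visits.
- Appendix A: questionnaire marked at six months, with no mode.
- Section 8.7: telephone and home contacts named, but not linked to the questionnaire.
- Section 11.5: query to the site investigator, which can retrieve a recorded value but not an unasked one.

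The EQ-5D note is the only place that says how the questionnaire reaches the patient.

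**2. How large could the shift be?** Let m be the share of living patients with no score and d the mean index in responders minus that in non-responders. The full mean is (1 − m) × responder mean + m × non-responder mean, so

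responder mean − full mean = m × d.

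Neither m nor d is in the documents. Two sets of assumptions give the range.

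*Set A, anchored on the Background.* For chronic limb-threatening ischaemia, section 4 states that "the one-year risk of limb amputation is 30" per cent. At a constant hazard the six-month risk is 1 − (1 − 0.30)^0.5 = 0.163, about 10 of 60 patients if all had that condition and about 5 if half did. Assume that 25% to 100% of amputees miss the questionnaire, that the limb-threatening share is 50% to 100%, and that d is 0.1 to 0.4:

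- low end: m = 0.5 × 0.163 × 0.25 = 0.020; shift = 0.020 × 0.1 = 0.002
- high end: m = 1 × 0.163 × 1 = 0.163; shift = 0.163 × 0.4 = 0.065

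*Set B, direct assumption on non-attendance.* Take m from 0.10 to 0.25 and d from 0.10 to 0.30:

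- low end: 0.10 × 0.10 = 0.01
- middle: 0.20 × 0.20 = 0.04
- high end: 0.25 × 0.30 = 0.075

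For scale, with an assumed SD of 0.25 to 0.30 and 48 responders (80% of 60), the standard error of the mean is 0.25/√48 = 0.036 to 0.30/√48 = 0.043. The middle case is thus about one standard error, the low ends are negligible and the high ends are material.

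**The case against.** The strongest reply is that the protocol does not restrict collection as tightly as it first appears. The request goes to all participating patients, the word 'only' is never attached to routine appointments, and section 8.7 shows that contact by telephone or at home was in mind. Using routine contacts is also a deliberate pragmatic choice in a registry, and quality of life appears in none of the section 5 objectives. This has force. It makes the point one of an unstated route for a minor outcome, not of a declared exclusion. It does not remove the point, because section 8.7 is not connected to the questionnaire and a site following section 8.3.1 would have no instruction for a patient without an appointment.

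Three stronger readings are tempting and are not supported:

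- *Amputees and inpatients will give no score.* Nothing says they go unasked. They may have more contact with the vascular team, not less.
- *Deaths distort the EQ-5D because of this rule.* A patient who has died gives no score under any mode of collection. How deaths, paired change and missing scores are summarised can be left to a statistical analysis plan, which is not shown here.
- *Confidence intervals will under-cover by a known amount.* Coverage follows entirely from the assumed inputs. In Set B it is about 80% to 85% at the middle case, about 94% at the low end (54 responders) and about 48% to 61% at the high end (45 responders). No single value can be attributed to this protocol.

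The 30% amputation risk also needs care. It applies to limb-threatening ischaemia, while section 7.2 also admits severe claudication without giving the mix, and it is not a non-attendance rate.

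**Conclusion.** The concern holds as a risk created by a stated collection rule. The one patient item that records cannot supply is tied to routine appointments, with no alternative given for it, and those who miss such an appointment are plausibly less well. The six-month quality-of-life summary may therefore be too favourable. The direction rests on that assumption about who misses appointments. The size rests on assumed shares missing and score gaps, and runs from near 0 to about 0.07 on the index, that is, from trivial to material. The primary patency outcome is not touched. This is a cheap improvement to a secondary outcome. It is best made before six-month collection, because no later analysis can recover questionnaires that were never put to patients.

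**What to change.** Amend the EQ-5D sentence in section 8.3.1 so that every living participant is asked for the questionnaire at the six-month time point whether or not an appointment takes place, by telephone or post where there is none. Record the mode of completion and the reason for any missing score in the case report form. Align section 8.7, so that it is clear whether the telephone and home contacts named there are used for the EQ-5D.

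The cost is a call or a posted form for the patients without an appointment: 6 to 15 of 60 if the share is 10% to 25% (0.10 × 60 to 0.25 × 60). No hospital visit is added, so the COVID-19 statement still stands. The downside is two modes of completion, which can shift scores slightly; recording the mode lets that be examined.

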8.3.2 Qualitative survey of the operators immediately after the procedure

All operators will be asked to fill in a survey relating to the procedure (intravascular lithotripsy) on the day that the procedure has taken place (online survey) using REDCap software. They will be questioned using multiple choice closed questions and open questions on the ease of the procedure, immediate peri-operative complications, and why they chose to use the devices that were used during the procedure, including the opinion/verdict of their multi-disciplinary meeting.

8.3.3 Optional Sub-study

A total of 20 consecutive patients will be invited to take part in sub-group analysis to document the impact of the intravascular lithotripsy on the calcified component of the atherosclerotic plaque. These patients will be recruited from the main site, University Hospitals of Leicester. We will stop recruiting in this sub-analysis once 20 patients have been recruited and have had their second CT scan three days after their intravascular lithotripsy procedure.

8.6 Randomisation and Codebreaking

This is a non-randomised study. Participants will be allocated a unique study identification number which will be site-specific, upon recruitment. This will be used in all CRFs.

8.7 Definition of End of Study

The end of study is the date of the last visit/ telephone follow up/ home visit of the last participant i.e. six months after the date the last patient has been recruited.

8.8 Discontinuation/Withdrawal of Participants from Study

Each participant has the right to withdraw from the study at any time. In addition, the investigator may discontinue a participant from the study at any time if the investigator considers it necessary for any reason including:

• Ineligibility (either arising during the study or retrospective having been overlooked at screening)

CONFIDENTIAL Page 19 of 35 SHOCC Study IRAS: 299307

- Significant protocol deviation
- Significant non-compliance with treatment regimen or study requirements
- An adverse event which requires discontinuation of the study or results in inability to continue to comply with study procedures
- Disease progression which requires discontinuation of the study or results in inability to continue to comply with study procedures
- Consent withdrawn
- Lost to follow up

The reason for withdrawal will be recorded in the CRF.

If the participant is withdrawn due to an adverse event, the investigator will arrange for follow-up visits or telephone calls until the adverse event has resolved or stabilised.

It is unlikely that adverse events will occur as this study follows national and international clinical guidance and standard NHS care pathways.

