8.3 Data collection

8.3.1 Main study

This study wishes to obtain the following routinely collected data from the patients' medical records and conduct further analyses* on routinely performed scans at various time points during patients' routine PAD care.

Baseline (pre intravascular lithotripsy) data collection:

- 1. Demographic information (age at time of recruitment, sex).
- 2. Weight/height, resting BP (anthropometric measurements).
- 3. Rutherford stage relating to PAD presentation.
- 4. Ankle brachial pressure index.
- 5. Baseline full blood count results and routine biochemistry, including total cholesterol levels, and lipid profile.
- 6. Baseline serum creatinine and estimated glomerular filtration rate.
- 7. Chronic kidney disease status.
- 8. Diabetes status, duration of diabetes history, and current diabetes medication(s).
- 9. History of previous major cardiovascular events.
- 10. Results of cross-sectional imaging relating to the arterial vasculature e.g. duplex or computed tomographic angiography*
- 11. Smoking status.
- 12. WiFi score.
- 13. Previous operations, including a full surgical and vascular history.
- 14. All concomitant medications as reported by patients.
- 15. Anonymised minutes from multi-disciplinary team meetings relating to the patients care.

Day of procedure (Post intravascular lithotripsy) data collection:

The data collected here will relate to information obtained during the intravascular lithotripsy

- 1. Exact location of the lesion treated,
- 2. Number and size(s) of intravascular lithotripsy catheters used
- 3. Duration of intravascular lithotripsy application per arterial site in seconds
- 4. Exact anatomy (number of occlusions or stenoses) of the arterial lesions present on intraoperative angiography
- 5. Nature of the additional surgical or endovascular treatments taking place
- 6. Duration of the whole procedure
- 7. Immediate complications during the procedure and steps taken to address them (e.g. thrombectomy)
- 8. Patency of the treated lesions
- 9. Level of operators performing the procedures
- 10. Volume of contrast used during the procedure.

Day of discharge data collection:

Where available, the data collected here will relate to the period between the completion of the intravascular lithotripsy procedure and the day of discharge

- 1. Re- interventions of any nature
- 2. Amputations of any nature
- 3. Ankle brachial pressure index.
- 4. Full blood count results and routine biochemistry.

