9. TREATMENT OF STUDY PARTICIPANTS

9.1 Description of Study Treatment

Patients will not receive any additional treatment as a result of taking part in this research. All patients taking part in this research will already have been offered treatment with intravascular lithotripsy (Shockwave) as part of their standard NHS care.

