11.7 Inclusion in Analysis

CONFIDENTIAL Page 24 of 35 SHOCC Study IRAS: 299307

All participants will be included in the final analysis as this is a pragmatic cohort study.

CONFIDENTIAL SHOCC Study IRAS: 299307

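### Section 8.8 permits outcome-related discontinuation from an observational study without saying that outcomes are still collected to six months

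*Protocol*

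**What the plan says.** Protocol section 8.8 gives a wide power: "the investigator may discontinue a participant from the study at any time if the investigator considers it necessary for any reason including". The reasons listed after it include:

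- "Disease progression which requires discontinuation of the study or results in inability to continue to comply with study procedures";
- "An adverse event which requires discontinuation of the study or results in inability to continue to comply with study procedures";
- "Significant non-compliance with treatment regimen or study requirements";
- significant protocol deviation, and ineligibility, including ineligibility found late.

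The reason is to be recorded in the CRF. For a participant withdrawn because of an adverse event, 8.8 provides visits or calls until that event resolves or stabilises. Section 10.2 adds an end of study assessment when an adverse event leads to withdrawal from treatment, but names neither a duplex scan nor a time for it.

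Other sections describe a study with little to discontinue from. Section 9.1: "Patients will not receive any additional treatment as a result of taking part in this research". Section 8.3.1: "This study wishes to obtain the following routinely collected data from the patients' medical records". The same section names the EQ-5D as the only item outside routine care; the optional sub-study in 8.3.3 adds a second CT scan.

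The primary outcome in section 6.2 is "patency of the treated arterial atherosclerotic lesion based on duplex ultrasound measurement at six months after the procedure has taken place". Section 11.7 says: "All participants will be included in the final analysis as this is a pragmatic cohort study". Section 11.2 expects all 60 patients to complete follow-up with full clinical and imaging data.

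**The concern.** The list in 8.8 reads like one written for a trial that gives a treatment. Here there is no regimen to comply with, and record review asks nothing of the participant.

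The listed grounds overlap with what the study measures. Worsening ischaemia or amputation is disease progression. Stroke, myocardial infarction and amputation are adverse events and also appear in the secondary objectives (section 5). These events need not be rare: the background (section 4) puts the one-year amputation risk in chronic limb threatening ischaemia at 30%.

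If participants are discontinued on these grounds and their six-month status is not obtained, the missing outcomes are informative. Patency would tend to be overstated, and events after discontinuation would be missed. Section 4 says that the results are meant to inform a later randomised trial, so an optimistic patency figure would carry forward into its planning.

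**Working it through.** **Comparing the sections**

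1. *Who may leave early?* Section 8.8: at the investigator's discretion. Progression and adverse events count only if they require discontinuation or prevent compliance with study procedures. Non-compliance and protocol deviation need only be significant.
2. *Which procedures need compliance?* Appendix A lists eligibility assessment, consent, the quality-of-life questionnaire, the sub-study CT and review of medical records. After consent, only the questionnaire and, for up to 20 patients, the CT ask anything of the participant. The power nevertheless covers discontinuation from the whole study.
3. *What is collected afterwards?* After an adverse event: follow-up of that event (8.8) and, on withdrawal from treatment, an end of study assessment (10.2). After progression, non-compliance or deviation: nothing is stated. Section 11.5 only provides for asking the site about missing or spurious data.
4. *What do the analysis sections expect?* Section 11.7 includes all participants. Section 11.2 expects 60 of 60 to complete, which is 0% attrition. No patency rate, dropout rate or formula accompanies the 60, so that number cannot be reproduced.

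**Illustration of size**

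From the protocol: N = 60. Assumed, because the protocol gives no rates: true patency p of 60%, 70%, 80% or 90%; a quarter or a half of failures lost; no patent lesions lost.

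Patent P = 60p; failures F = 60 − P; L = failures lost from the denominator. Observed patency = P / (60 − L). Bias = P / (60 − L) − P / 60.

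| True patency | F | L (about a quarter) | Observed | Bias | L (half) | Observed | Bias |
|---|---|---|---|---|---|---|---|
| 36/60 = 60% | 24 | 6 | 36/54 = 66.7% | 6.7 | 12 | 36/48 = 75.0% | 15.0 |
| 42/60 = 70% | 18 | 4 | 42/56 = 75.0% | 5.0 | 9 | 42/51 = 82.4% | 12.4 |
| 48/60 = 80% | 12 | 3 | 48/57 = 84.2% | 4.2 | 6 | 48/54 = 88.9% | 8.9 |
| 54/60 = 90% | 6 | 2 | 54/58 = 93.1% | 3.1 | 3 | 54/57 = 94.7% | 4.7 |

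Bias is in percentage points. A quarter of 18 is 4.5 and a quarter of 6 is 1.5; these were taken as 4 and 2. The range is about 3 to 15 points.

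At 70% true patency with half of the failures lost, the Wilson 95% interval moves from 57.5–80.1% (42/60) to 69.7–90.4% (42/51).

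If the six-month status of every discontinued participant is obtained, L = 0 and the bias is zero in every row.

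**The case against.** A reader might infer that 8.8 contradicts 11.7. It does not. Section 8.8 governs who may be discontinued from the study, section 11.7 who is analysed, and 8.8 excludes nobody from analysis. A participant discontinued early can still be counted if the status is obtained or a rule assigns one. Such a rule commonly belongs to the analysis plan, so its absence here is not held against the protocol.

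A reader might also infer that 8.8 removes patency failures. The text says only that the investigator may discontinue, and it attaches a condition to progression and adverse events. With so few procedures to comply with, that condition may seldom be met.

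Nor is follow-up of the adverse event the only provision after withdrawal, given the end of study assessment in 10.2. An amputation or re-intervention that led to discontinuation should already be on the CRF, because 10.2 requires all adverse events to be recorded and section 8.3.1 collects these events at discharge and 30 days. Only later events are at risk.

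All of this stands, and it limits the point to a permitted risk. It does not remove the point. The section 10.2 assessment covers one ground and need not supply a six-month duplex result. For the other grounds the protocol does not say that collection continues. An analysis plan can classify a missing outcome but cannot collect it.

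**Conclusion.** The point holds as a weakness in the follow-up rules. Section 8.8 allows discontinuation on grounds plausibly related to loss of patency and leaves open whether outcomes are collected afterwards. That is in tension with 11.7 and with the full completion expected in 11.2.

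The likely direction is upward for six-month patency, with undercounting of amputations, re-interventions and readmissions that occur after discontinuation. The 3 to 15 points are an illustration and not an estimate. They rest on assumed patency and loss rates, on only failures being lost, and on those participants having no six-month status and leaving the denominator. If patent lesions were lost as well, the bias would be smaller.

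**What to change.** Reword section 8.8 as follows:

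- Separate withdrawal of consent from every other reason.
- State that disease progression, adverse events, non-compliance, protocol deviation and late-found ineligibility do not end follow-up. Report the last two as deviations.
- State that routine duplex results and the other outcomes continue to be collected from medical records to six months.
- State that only withdrawal of consent to the use of records ends collection, and that data up to that date are kept.

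Bring the withdrawal wording in 10.2 into line. It refers to a section 7.7, although section 7 ends at 7.3.

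The cost is a wording change and possibly a matching line in the consent form. It needs no extra visits and does not alter clinical care.
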